If motivation to adhere to the BLT protocol is lacking, coaches will employ brief MI. Many of our behavioral health and assessment (BAC) staff have delivered MI and adherence promotion protocols similar to this for previous trials. While BAC staff have prior MI experience, they will also attend MI workshops offered by KPNW and will then be trained by senior staff to address MI specifically for BLT use. We have engaged a MI fidelity expert, [name] to rate training cases and ongoing calls to confirm initial and ongoing coach MI fidelity. During start-up each coach will conduct several simulated BLT coaching calls; [name] will rate audio recordings of these simulations for MI quality/adherence. Staff who are rated 4 or higher on four global components of MI quality/adherence for these initial simulations will be cleared to conduct study MI with enrolled participants. We will also conduct ongoing MI fidelity ratings for study Arm 3 phone coach contacts. [name] will conduct MI fidelity reviews of a random 10% selection of these Arm 3 coaching calls (blocked by coach, and by early/late session). Additionally, as [name] reviews MI sessions she will also complete fidelity checklists (to be created and submitted in a subsequent modification) of BLT health education review/practice and problem solving that coaches may deliver to promote ideal BLT sessions (e.g., did coach review whether daily BLT sessions occurred? If not, were barriers identified and possible solutions explored?). [name] MI fidelity and BLT education ratings will be used as process variables, but also to provide feedback to coaches during supervision meetings.

Based on prior coaching experiences, ~10% of individuals randomized to Arm 3 will likely not engage with coaches, despite indicating a previous willingness to do so. Coaches attempt to reach all Arm 3 participants, but after 3 failed outreach attempts coaches will send a final "contact us if you wish" email or letter.

Assessments

We will ask participants to complete baseline and follow-up surveys using the REDCap online survey system; those who do not complete the online surveys after 3 prompts will be called by interviewers and verbally administered the same scales. Assessments consist of the baseline assessment; a post-acute treatment assessment at 2 months after enrollment; and follow-up assessments at month 4 and month 6, for a total of 4 data points over the course of six months. Interviewers will be blinded to study condition.

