# INTRODUCTION

This statistical analysis plan provides guidelines for the final presentation and analysis for the BLT Pilot Trial. The R34 pilot was designed to prepare for a future, fully-powered effectiveness trial. This study collects information to conduct the BLT Pilot Trial as described in these following aims:

Aim 1.1: We will enroll 90 depressed patients in this modest-size feasibility pilot, and randomize them to:

- Arm 1: Treatment as Usual (TAU) control: A “usual care” control group (e.g., antidepressants, watchful waiting, psychosocial therapy; all TAU will be recorded for all participants in all study conditions); or
- Arm 2: TAU + Minimal BLT Encouragement: TAU plus two minimal communications (mailed letter, secure EHR message) identifying BLT as a promising treatment, and outlining steps for patients to self-initiate. Arm 2 will not include any phone coaching or adherence promotion.
- Arm 3: TAU + Enhanced BLT Encouragement + Adherence Promotion + MI: TAU plus 2-4 brief calls to encourage BLT use, advise on purchase of a light box (LB), assist with obtaining insurance reimbursement, educate for correct LB use, and provide motivational interviewing (MI) as needed to promote adherence.

Aim 2. This small pilot sample is insufficient for confirmatory tests. However, we will conduct analyses that mirror those planned for a future, fully-powered trial. Key analytic contrasts are (a) active Arms 2 + 3 vs. control Arm 1; (b) each active Arm (2, 3) separately vs. control Arm 1; and (c) Minimal Arm 2 vs. Enhanced Arm 3. For each contrast we will initially examine differences between study arms in pre-post change in proposed mediators in BLT and MI effects; followed by examination of differences in pre-post change in the primary (PHQ-9) and key secondary outcomes (see Assessment). We then examine candidate mediators (improved sleep, normalized circadian rhythm, increased physical activity, readiness for change) for mediating BLT and MI effects on depression. We will also examine moderation of BLT effects and subgroup outcome variation (e.g., receiving vs. not receiving TAU ADs). Pilot feasibility data will facilitate rapid launch of a future trial: estimated recruitment, retention, and adherence with BLT protocol; and a cautious estimate (with wide confidence intervals) of BLT effectiveness.

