# BACKGROUND

## Rationale and research questions

BLT Pilot aims to test the feasibility of conducting a controlled clinical trial designed to evaluate the effectiveness and cost-effectiveness of minimal and enhanced “encouragement” to initiation and regular use BLT for treatment of an incident unipolar depressive episode among adult members of the KPNW medical plan. Encouragement includes motivational interviewing, education, and tools for using BLT with high adherence.

Our primary clinical outcome is the PHQ-9 at post-acute treatment (2 months follow-up). Our primary process outcomes are initiation of BLT therapy and adherence to best BLT practices.

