## Hypotheses

While this is a pilot study and not powered to assess intervention effects, we hypothesize that the combined intervention (minimal + enhanced encouragement arms) will have larger reductions in PHQ-9 at post-acute treatment than the TAU control arm; and that enhanced encouragement will have larger reductions in PHQ-9 at post-acute treatment than minimal encouragement.

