## Preliminary data evaluation

Before any analyses, we will conduct procedures to assess data quality and completeness and will evaluate missing data patterns. In order to maximize analytic team efficiency, we will audit data from the initiation of data collection. Careful descriptive analyses (e.g., mean, SD, range, skewness) will be conducted for all study variables of interest. We will evaluate distributions to ensure that they meet the assumptions of planned analyses (below), including the detection of outliers (another potential indicator of entry error). As noted early, this proposed R34 pilot is underpowered to perform formal tests of effectiveness. However, we will conduct analyses as we would for a fully-powered, R01-funded project, both to demonstrate feasibility and to generate effect size estimates for the future, fully powered randomized trial—subject to the limits and cautions of using pilot data for this purpose (e.g., use with very wide confidence intervals)[1-3].

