## Analysis of primary outcome

For our PHQ-9 primary outcome, we will test whether there are differences in score trajectories across time between arms with two-level hierarchical linear models (HLMs) in a growth curve framework[7-9]. The first level of the model will include time as a predictor, modeling within-person variation. The second level will include a dummy variable for arm (e.g., 1=TAU+BLT+AP or TAU+BLT, 0=TAU) as the predictor variable for both the random effects of the intercept and slope for time. A significant coefficient for arm on the time slope would indicate that there are different trajectories across time for BLT arms versus TAU. We will probe any significant arm x time interactions by graphing the simple-effects equations to determine whether the observed pattern is consistent with hypotheses. Compared to the Arm 1 TAU condition, a pattern in which the active arms (Arms 2 and 3) exhibit a greater PHQ-9 decrease over time supports the effectiveness of the intervention. However, recall this pilot is insufficiently powered to formally test intervention effects[1-3].

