## Power analysis, sample size

The R34 pilot funding cap limits us to a feasibility sample that is insufficient for an adequately powered test of the hypothesis. Nonetheless, we provide an estimate of the statistical power obtained from this sample of 90 participants. Meta-analyses suggest an overall effect size for BLT of  $d=0.84$ [14]. We conservatively estimate the effect size likely to be obtained in this pilot trial as lower than reported in meta-analyses because this is a real-world effectiveness population; even with Arm 3 adherence promotion BLT adherence is likely to be lower than in efficacy trials, leading to lower clinical benefit. Assuming a retained sample size of  $N=81$  at the final 6-month assessment, we conducted power analysis for the HLM of the primary outcome (using SAS version 9.4) to determine the minimum detectable effect size. At a two-tailed alpha level of .05 and conservatively assuming an autocorrelation of .70, we would have 80% power to detect a Cohen's  $d$  for the time by arm effect as small as 0.39 for the contrast between active intervention arms (Arms 2 and 3) and TAU, and as small as 0.55 for contrasts between individual arms; both estimates are medium effects.

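### The SAP sets the primary outcome and both hypotheses at PHQ-9 month 2, but the primary analysis reads the effect from an arm-by-time slope and specifies no month-2 estimate

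*SAP*

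**What the plan says.** **Declared target.** The SAP (Rationale and research questions) states: "Our primary clinical outcome is the PHQ-9 at post-acute treatment (2 months follow-up"). Under Hypotheses, the combined active arms are expected to show "larger reductions in PHQ-9 at post-acute treatment than the TAU control arm", and "enhanced encouragement will have larger reductions in PHQ-9 at post-acute treatment than minimal encouragement". The protocol (section 6, Assessments) confirms the timing: "a post-acute treatment assessment at 2 months after enrollment; and follow-up assessments at month 4 and month 6".

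**Planned analysis.** The SAP (Analysis of primary outcome) specifies a two-level hierarchical linear model with time at level 1 and an arm dummy acting on the random intercept and slope. The effect is read as follows: "A significant coefficient for arm on the time slope would indicate that there are different trajectories across time for BLT arms versus TAU". The only follow-up is graphing, and only when the interaction is significant. The example dummy codes active arms against TAU; none is given for Arm 3 against Arm 2. The protocol's section of the same name has the same model, and the protocol names PHQ-9 as primary without a visit.

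**Related text.** The power section takes N=81 "at the final 6-month assessment, we conducted power analysis for the HLM of the primary outcome". Aim 2 in the SAP Introduction lists, for each key contrast, mediators first, "followed by examination of differences in pre-post change in the primary (PHQ-9) and key secondary outcomes", with no visit and no model. The SAP (Preliminary data evaluation) says the analyses serve "to generate effect size estimates for the future, fully powered randomized trial".

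**The concern.** The outcome and hypotheses concern the arm difference in PHQ-9 at one visit. The coefficient on the time slope is the monthly rate at which the arms separate, averaged over whichever visits enter the model. The two agree only if the arm difference grows in a straight line from baseline.

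The protocol gives reason to doubt a straight line. It describes antidepressant action within 1-2 weeks, an acute period of 2 months, and then a less intense maintenance phase meant to sustain the benefit. That suggests an early rise and then a plateau.

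Followed as written, the plan would report a different quantity from the one it declares primary. The cost falls mainly on planning the full trial: if the slope is the effect carried forward, it is not the month-2 effect.

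**Working it through.** **Inputs from the documents.** Visits at 0, 2, 4 and 6 months; 1:1:1 allocation; 81 retained, so 27 per arm and 54 vs 27 for Arms 2+3 vs Arm 1; two-sided alpha 0.05; autocorrelation 0.70; stated detectable d of 0.39 (combined contrast) and 0.55 (individual arms).

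**Assumptions, not in the documents.** The shape of the effect over time; D, the benefit at month 2 in baseline SD units; the variance components (intercept variance 0.7, residual variance 0.3, random-slope SD 0 to 0.10 baseline SD per month). Power uses the normal approximation.

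**1. The plan's own figures.** Detectable d = (1.96 + 0.84) × sqrt(1/n1 + 1/n2) × sqrt(1 − 0.7²).
- 27 vs 27: 2.80 × 0.272 × 0.714 = 0.545, which matches 0.55.
- 54 vs 27: 2.80 × 0.236 × 0.714 = 0.47, not 0.39. The value 0.39 appears with 54 vs 54 (0.385).

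No variant tried gives both figures. The documents do not say how d is standardised. This is a separate matter, and the point here does not depend on it.

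**2. What the slope estimates.** With a random intercept and slope, independent residuals and complete data, the generalised least squares slope equals ordinary least squares whatever the variance components. Deviations of time from its mean of 3 are −3, −1, 1, 3, with sum of squares 20, so the weights are (−3, −1, 1, 3)/20. For an effect reached at month 2 and held (0, D, D, D):
- slope = (−1 + 1 + 3)D/20 = 0.15D per month
- arm-on-intercept term = 0.75D − 3 × 0.15D = 0.30D
- slope × 2 = 0.30D; fitted month-2 gap = 0.30D + 0.30D = 0.60D; slope × 6 = 0.90D.

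| Assumed effect at 0, 2, 4, 6 | True month 2 | Slope × 2 | Fitted month 2 | Slope × 2, AR(1) 0.7 | Fitted month 2, AR(1) 0.7 |
|---|---|---|---|---|---|
| 0, D, D, D (held) | D | 0.30D | 0.60D | 0.33D | 0.45D |
| 0, D, 0.75D, 0.5D (halved) | D | 0.125D | 0.50D | 0.16D | 0.31D |
| 0, D, 0.5D, 0 (gone) | D | −0.05D | 0.40D | −0.006D | 0.18D |
| 0, 0, 0.5D, D (late only) | 0 | 0.35D | 0.20D | 0.335D | 0.275D |

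For the held effect under AR(1), slope × 6 is 0.99D.

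**3. Power at D = 0.5, held, 54 vs 27** (1/54 + 1/27 = 0.0556), baseline arm means left free:
- Slope, no random-slope variance: effect 0.075, SE = sqrt(0.3/20 × 0.0556) = 0.0289, power 74%. With random-slope SD 0.05, 0.07 and 0.10 it is 67%, 61% and 52%; under AR(1), 45%.
- Month-2 change score: SE = sqrt(0.6 × 0.0556) = 0.183, power 78%, falling to 76% at slope SD 0.10.
- Month 2 adjusted for baseline: SE = sqrt(0.51 × 0.0556) = 0.168, power 84%, falling to 82%.

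If the effect halved by month 6, slope power is 13-19%. If instead it grows linearly and reaches D only at month 6, slope power is 82% with no random-slope variance.

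**4. Detectable d for the month-2 contrast** (80% power, baseline-adjusted, correlation 0.7): 0.47 (54 vs 27) and 0.545 (27 vs 27) with 81 retained; 0.45 (60 vs 30) and 0.52 (30 vs 30) if all 90 are seen at month 2.

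**The case against.** **Time coding is unstated.** If only baseline and month 2 entered the model, the slope would give the month-2 change. If time were centred at month 2, the arm-on-intercept coefficient would be the model's month-2 difference. Neither is written down. The growth-curve framing, the four visits and the month-6 power basis all point to one slope over all visits. The uncertainty stands as a reason to state the coding.

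**The aims promise pre-post change.** Baseline to month 2 is a reasonable reading of Aim 2, and it covers every key contrast. It still lacks a visit, a model and an interval. A month-2 gap could also be derived from the fitted line, but the plan does not ask for it, and it is right only if the arms diverge linearly.

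**The power comparison is partly about baseline handling.** This is correct. Setting 84% against 74% changes two things at once. With baseline means free in both, the figures are 78% and 74%. With baseline means constrained equal in both, the slope has 87% against 84% for month 2 when there is no random-slope variance. It has 81%, 75% and 64% at slope SD 0.05, 0.07 and 0.10, and 68% under AR(1), against 82-84% for month 2. The halved-effect figure of 13-19% becomes 21-33%. Power alone therefore does not decide the matter.

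**Fading is not predicted.** The documents plan maintenance to sustain benefit, and a sustained benefit is still detected by the slope. What is lost is its month-2 size.

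**It is a pilot.** The plan disclaims formal testing and calls its effect sizes highly tentative. That limits how serious the point is but does not remove it.

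**Conclusion.** The concern holds, as something that should be fixed rather than a fatal flaw. The declared primary outcome and both hypotheses are at month 2; the specified effect measure is a slope; no month-2 contrast with a model and interval is given for either hypothesis. For an effect reached by month 2 and held, the slope's two-month change is 0.30D to 0.33D and the fitted month-2 gap 0.45D to 0.60D, depending on the error structure. These fractions rest on the assumed effect shape and on reading time as linear over all four visits. The conclusion rests on the mismatch of quantities, not on a loss of power.

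**What to change.** - State the time coding and the visits that enter the model.
- Keep the mixed model, but enter visit as categorical (0, 2, 4, 6) with arm-by-visit terms and unstructured within-person covariance. Constrain baseline means equal across arms, or use baseline PHQ-9 as a covariate.
- Make the month-2 arm difference with its 95% CI the primary estimate for both hypotheses, Arms 2+3 vs Arm 1 and Arm 3 vs Arm 2, and give the arm coding for each.
- Keep months 4 and 6 and the linear slope as secondary.
- Restate the detectable effect for the month-2 contrast, using the values in step 4 of the working or the sponsor's own inputs.
- Say which estimate goes forward to plan the full trial.

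If the sponsor in fact wants the 0-6 month trajectory, the alternative is to restate the SAP's outcome and hypotheses that way. Either way, outcome and analysis must name the same quantity.

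**Cost.** Wording in the SAP and the protocol's analysis section only, since month-2 data are already collected. The model has a few more parameters with about 90 people and four visits, and it has less power than the slope if the benefit keeps growing in a straight line to month 6.

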## Moderation and mediation

In addition to primary outcome analyses we will conduct exploratory analyses of moderation using variables identified through previous research and clinical expertise, specifically indication of pharmacotherapy use (1=yes, 0=no), age (continuous), gender (1=female, 0=male), race and ethnicity (1=racial/ethnic minority, 0=non-Hispanic white), baseline PHQ-9 (1=clinically elevated, 0=below clinical range), and EHR indication of mental health comorbidities such as eating disorders, anxiety (1=comorbidity, 0=no comorbidity). Moderation will be indicated by a significant time x arm x moderator interaction in HLM.

We propose to conduct exploratory analyses of the BLT mediation pathway as the extent to which the relation between BLT and outcomes is mediated by changes in participants' 1) sleep (sleep diary and actigraphy, and ISI subjective sleep quality), 2) total physical activity, and 3) circadian timing and chronotype. For example, to evaluate the mediating effect of ISI sleep quality we will regress post-acute treatment ISI on baseline ISI and a randomization condition indicator; and we will regress follow-up PHQ-9 at post-acute treatment ISI and a randomization condition indicator. Using the product coefficients mediation approach, we will use the resulting regression coefficients and standard errors (SEs) to estimate the indirect effect[10-12]. Because SEs of the products of regression coefficients are not normal, we will use bias-corrected bootstrapping to estimate the SEs for the indirect effect.[12] We will use a similar approach for the MI pathway to test the mediating effect of participants' increased readiness to change on BLT adherence.

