- Active EHR diagnoses and prescriptions representing any of the following contraindications for BLT: Conditions that might render skin or eyes more vulnerable to phototoxicity (e.g., ophthalmic disorders such as cataract, macular degeneration, glaucoma, retinitis pigmentosa; disorders affecting the retina such as retinopathy, diabetes, herpes); or photosensitive skin; or if they are taking a photosensitizing medication or herb (e.g., St. John's wort or a psoralen).
- EHR-recorded diagnoses of bipolar disorder I or II.

Screening inclusion criteria:

- Elevated PHQ-9 (score of 10 or higher);
- Able and willing to conduct study assessments and phone coaching in English;
- Phone and internet access.

Screening exclusion criteria:

- Participation barriers (e.g., terminal end-stage cancer, moving out of the region, no locator information);

- Contraindicated diagnoses or medications (see EHR exclusion criteria above) in case these are known to patients but are not EHR-recorded (e.g., if they were diagnosed with a contraindicated condition before becoming a KP member and have not yet sought care for it);
- Contraindicated diagnoses or medications (see EHR exclusion criteria) newly reported that were not captured in the EHR;
- Emergent bipolar, manic, mixed symptoms that may not have been formally diagnosed yet (e.g., significant mood swings, excessive increases in energy, dramatically less need for sleep).

In the event of a screen failure, or when a potential participant is contacted but declines participation, minimal demographic data collected (such as age, sex, race, ethnicity), and reason for declining will be retained for review. This data may help inform future study design.

c. Vulnerable Populations

Vulnerable Populations (VPs)	Include/Exclude	Rationale
Pregnant women	Include	Pregnancy has no known vulnerabilities for BLT. Further, BLT may be a valuable alternative treatment for pregnant women who might be hesitant to take antidepressants.
Children	Exclude	N/A
Neonates of uncertain viability or nonviable neonates	Exclude	N/A
Prisoners	Exclude	N/A

d. Setting

This study will be conducted by study staff at Center for Health Research (CHR), among the KPNW adult membership. Participants will be able to conduct all study activities from home.

e. Recruitment Methods

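### Exploratory moderation is still judged on significance alone, for six moderators: about a one-in-four chance of a false flag on the pooled contrast, and low power for a real moderator

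*SAP*

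**What the plan says.** The SAP, under Moderation and mediation, states that "we will conduct exploratory analyses of moderation using variables identified through previous research and clinical expertise". The first four variables are "indication of pharmacotherapy use (1=yes, 0=no), age (continuous), gender (1=female, 0=male), race and ethnicity (1=racial/ethnic minority, 0=non-Hispanic white"; the other two are "baseline PHQ-9 (1=clinically elevated, 0=below clinical range), and EHR indication of mental health comorbidities such as eating disorders, anxiety (1=comorbidity, 0=no comorbidity". The rule for reading the results is "Moderation will be indicated by a significant time x arm x moderator interaction in HLM". The protocol has the same text in section 6, Data Analysis.

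Aim 2 in the SAP Introduction lists four contrasts: "Key analytic contrasts are (a) active Arms 2 + 3 vs. control Arm 1", then "b) each active Arm (2, 3) separately vs. control Arm 1; and (c) Minimal Arm 2 vs. Enhanced Arm 3". It mentions moderation of BLT effects but does not tie the moderators to particular contrasts. The SAP also says, under Preliminary data evaluation, that the pilot is "underpowered to perform formal tests of effectiveness". On entry, the protocol's screening criteria require "Elevated PHQ-9 (score of 10 or higher" points.

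Neither document gives an interval-based reading, a count of tests, a multiplicity rule or a power figure for moderation.

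**The concern.** The plan mostly treats the pilot as a source of cautious estimates. The moderation sentence does something else: it lets a p-value indicate which variables moderate the effect. With six candidates, some will cross 0.05 by chance. Interactions are also estimated much less precisely than main effects, so a real one will often not cross it. A pilot report written to this rule could name a chance moderator, pass over a real one, and overstate the size of whatever it names.

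**Working it through.** **Inputs from the documents.** Six moderators (SAP, Moderation and mediation). Two-sided alpha 0.05, autocorrelation 0.70, retained N = 81, and detectable effects at 80% power of 0.39 (pooled) and 0.55 (single-arm contrasts) (SAP, Power analysis). Allocation is 1:1:1 (protocol section 6, Randomization), so 27 per arm. The SAP gives no separate alpha for moderation, so 0.05 is carried over.

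**Assumptions.** Binary moderators with prevalence 50%, 30% or 20%; moderators independent, or correlated up to 0.5; normal approximation.

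**Step 1: the plan's own figures.** Detectable effect = (1.96 + 0.84) × f × √(1/n1 + 1/n2). The SAS program is not given. With f = √(1 − 0.70²) = 0.714:
- 27 v 27: 0.545, which matches the stated 0.55.
- 54 v 27: 0.472, which does not match the stated 0.39.

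With equal arms and a common variance, the pooled-to-single ratio is √(1/54 + 1/27) / √(2/27) = 0.866 whatever f is. The stated ratio is 0.39/0.55 = 0.709. If 0.55 is right, the pooled figure is 0.55 × 0.866 = 0.476. Both 0.39 and 0.476 are carried forward.

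**Step 2: chance of at least one false flag when nothing moderates.**
- Pooled contrast, six independent moderators: 1 − 0.95⁶ = 26.5%.
- Pooled contrast, five usable moderators: 1 − 0.95⁵ = 22.6%.
- Pooled contrast, six moderators correlated 0.2, 0.3, 0.5 (simulated): 25%, 24%, 21%.
- All four contrasts, which share arms: a simulation of 2,000,000 draws gives 12.8% per moderator, so 1 − (1 − 0.128)⁶ = 56.0%. With correlations of 0.2, 0.3, 0.5 it is 54%, 52%, 45%. With five independent moderators it is 49.5%. Treating the 24 tests as independent would give 1 − 0.95²⁴ = 70.8%, which overstates it because the contrasts overlap.

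**Step 3: power for a real interaction.** For a binary moderator with prevalence q, the interaction SE is 1/√(q(1 − q)) times the main-effect SE: 2.00, 2.18 and 2.50 at 50%, 30% and 20%. At a 50:50 split the interaction detectable with 80% power is therefore 2 × 0.39 = 0.78, 2 × 0.476 = 0.95, or 2 × 0.55 = 1.10. Power = Φ(2.80 × d/(detectable effect × inflation) − 1.96), plus a negligible opposite tail.

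| Contrast (detectable main effect) | True interaction | q = 50% | 30% | 20% |
|---|---|---|---|---|
| Pooled (0.39) | 0.39 | 29% | 25% | 20% |
| Pooled (0.476) | 0.39 | 21% | 18% | 15% |
| Single arm (0.55) | 0.55 | 29% | 25% | 20% |
| Pooled (0.39) | 0.84 | 85% | 79% | 67% |
| Pooled (0.476) | 0.84 | 70% | 62% | 51% |
| Single arm (0.55) | 0.84 | 57% | 50% | 40% |

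The value 0.84 is the published overall effect of BLT that the plan cites. Age is continuous, so the prevalence formula does not cover it.

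**Step 4: size of a flagged estimate.** At a 50:50 split on the plan's pooled figure, significance needs an estimate of at least 1.96 × 2 × 0.39/2.80 = 0.55. A true interaction of 0.39 is flagged in the right direction only when overestimated by 40% or more.

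**The case against.** The case against is substantial. The analyses are labelled exploratory in the sentence that introduces the moderators, and the SAP says more than once that the pilot cannot support formal tests. Rehearsing the future trial's analyses is a stated purpose. The main effect has the same kind of significance rule, so moderation is not singled out. Uncorrected tests in a labelled exploratory analysis are common. All of this stands, and it is why the point is minor.

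The caveats do not reach the rule itself, however. The wide-interval caution under Use of pilot results concerns the between-condition effect size. The SAP follows its main-effect rule with a reminder of low power, but not its moderation rule. The protocol's power section says the pilot is not powered for mediation and is silent on moderation.

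Four stronger readings are tempting but not supported:
- A reader might infer that a false moderator is more likely than not. That needs every moderator tested on all four contrasts. The documents do not say so, and the example arm coding is the pooled one.
- A reader might infer a breach of error control. No confirmatory claim is made.
- A reader might infer that flagged moderators will set the next trial's eligibility or strata, or that a non-significant one will be called absent. Neither is written.
- A reader might infer that baseline PHQ-9 has no variation. Entry at 10 or more makes a small or empty lower category possible, but the cut-off for clinically elevated is not given and the baseline survey follows screening.

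**Conclusion.** The concern holds as a minor point. A significance-only rule sits inside an analysis that the plan itself calls exploratory and low in power. On the narrowest reading, the pooled contrast alone, it flags a chance moderator in about 26% of trials when nothing moderates the effect and the moderators are independent, or about 23% with five usable moderators. The 45% to 56% range applies only if all four contrasts are used, and depends on how correlated the moderators are.

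An interaction as large as the main effect the trial was sized on is found about 20% to 29% of the time, or 15% to 21% on the pooled contrast if the consistent figure of about 0.48 applies. Moderator prevalences are assumed. A much larger interaction, equal to the whole published effect, would be found 40% to 85% of the time, so the statement about missed moderators is limited to effects of the size planned for.

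**What to change.** In the SAP (Moderation and mediation) and the protocol (section 6, Data Analysis), replace the decision sentence with:

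> Moderation analyses are exploratory and will use the pooled contrast (Arms 2+3 vs 1), with any other contrast listed. For each moderator the time x arm x moderator estimate will be reported with its 95% CI (for binary moderators also the arm effect in each level; for age, per unit of age). The number of tests will be stated, and no moderator will be judged present or absent on significance alone.

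In the same edit, state the baseline PHQ-9 cut-off and confirm that both categories can occur, or enter the score as continuous. The mismatch between 0.39 and 0.55 should be resolved separately in the power section.

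The cost is a few extra reported estimates from the same models. The pilot also gives up naming moderators by p-value.
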